4.4.1.1.5 Number of Days of Occurrence

Number of days of occurrence over the period considered is derived from the daily intensities computed as described in [Section 4.4.1.1.1](#). It corresponds to the number of days with daily intensities of Grade 1, Grade 2, or Grade 3. Number of days of occurrence on the solicited period with a specified intensity may also be derived.

4.4.1.1.6 Overall Number of Days of Occurrence

If a reaction is ongoing at the end of the solicited period, then the overall number of days of occurrence is derived from the daily intensities and the stop date of the reaction after the end of the solicited period. The overall number of days of occurrence is:

- (stop date – last vaccination date) + (number of days of occurrence within the solicited period) – length of the solicited period + 1

If the stop date is missing or incomplete (contains missing data [MD]), the overall number of days of occurrence will be considered as Missing.

4.4.1.1.7 Ongoing

Ongoing is derived from the last daily intensity of the solicited period computed as described in [Section 4.4.1.1.1](#) and the maximum intensity on the ongoing period. The investigator's ongoing flag is not used because the measurement would determine the ongoing status of the reaction.

If the last daily intensity of the solicited period is at least Grade 1 and maximum intensity on the ongoing period is also at least Grade 1, then the reaction is considered ongoing. In any other cases the reaction will not be considered as ongoing.

4.4.1.2 Unsolicited Non-serious AEs

4.4.1.2.1 Presence

An observation will be considered an event if it has at least a verbatim term and is not a Grade 0 intensity event. Grade 0 events should be included in the listing “Unsolicited non-serious AEs not included in the safety analysis.”

4.4.1.2.2 Intensity

Intensity for unsolicited non-serious AEs will be derived according to the following classification: None, Grade 1, Grade 2, Grade 3, or Missing.

If the unsolicited non-serious AE is measurable and its preferred term is part of the list of solicited reactions, then the measurement is derived based upon and following the same rule as the intensity scales defined in [Section 4.4.1.1.1](#) for that measurable injection site or systemic reaction.

Intensity for the other unsolicited non-serious AEs will correspond to the value reported in the CRF.

The maximum intensity corresponds to the highest intensity for a unique term.

4.4.1.2.3 Last Vaccination

Last vaccination before any unsolicited non-serious AE is the study vaccination at V01.

4.4.1.2.4 Time of Onset

Time of onset is derived from the start date of the unsolicited non-serious AE provided in the clinical database and the date of last vaccination:

- start date of the unsolicited non-serious AE – date of previous vaccination

The time of onset should be considered as missing only if one or both of the dates are missing or partially missing.

The unsolicited non-serious AEs will be analyzed “Within 30 days”, which corresponds to AEs with a time of onset between 0 and 30 days after vaccination or missing. An AE with missing time of onset will be considered to have occurred just after the vaccination indicated by the visit number, so will be included in these tables.

Note: Unsolicited non-serious AEs that occurred before vaccination (negative time of onset) or with a time of onset higher than defined above will not be included in analysis, but will be listed separately.

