3.1 Trial Design

This is a Phase III, modified double-blind, randomized, parallel-group, active-controlled, multi-center trial to evaluate the immunogenicity and describe the safety of MenACYW conjugate vaccine compared to the MENVEO[®] in healthy children 2 to 9 years of age in the United States.

Healthy, meningococcal-vaccine naïve children aged 2 to 9 years will be randomized in a 1:1 ratio as follows:

- Group 1: MenACYW conjugate vaccine: N = 500
 - Group 1a: 250 children 2 to 5 years of age^a
 - Group 1b: 250 children 6 to 9 years of age^b
- Group 2: MENVEO[®]: N = 500
 - Group 2a: 250 children 2 to 5 years of age^a
 - Group 2b: 250 children 6 to 9 years of age^b

All subjects will provide blood samples for immunogenicity assessment at baseline (pre-vaccination) and at 30 to 44 days after vaccination.

Solicited adverse event (AE) information will be collected for 7 days after vaccination; unsolicited AE information will be collected from Visit 1 (Day [D] 0) to Visit 2 (D30 [+14 days]) and serious adverse event (SAE) information [REDACTED] will be collected throughout the study period from D0 through D180 (+14 days) after vaccination.

Medically-attended adverse events (MAAEs) will be collected throughout the study from Visit 1 through Visit 2 (as part of the collection of unsolicited AE information) and from Visit 2 through D180 (+14 days) (as MAAEs).

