3.2 Trial Plan

A schedule of assessments and study vaccinations is provided in the Table of Study Procedures.

Vaccination

All subjects will receive a single dose of either MenACYW conjugate vaccine or MENVEO[®] at Visit 1 (D0).

Blood Sampling

All subjects will provide a pre-vaccination blood sample at D0 and a post-vaccination sample at Visit 2 (30 to 44 days after the vaccination at Visit 1).

^a “2 to 5 years of age” means from the day of the 2nd birthday to the day before the 6th birthday

^b “6 to 9 years of age” means from the day of the 6th birthday to the day before the 10th birthday

Antibodies to meningococcal serogroups A, C, Y, and W antigens will be measured by hSBA for all subjects, and by rSBA for a subset of subjects.

Table 3.1: Testing strategy for *N meningitidis* serogroups A, C, Y, and W

	ACYW serogroups tested by hSBA* (all subjects)	ACYW serogroups tested by rSBA† (subset)
Group 1		
Group 1a (2 to 5 years old)	250	100
Group 1b (6 to 9 years old)	250	100
Group 2		
Group 2a (2 to 5 years old)	250	100
Group 2b (6 to 9 years old)	250	100

* hSBA: serum bactericidal assay using human complement

† rSBA: serum bactericidal assay using baby rabbit complement

Collection of Safety Data

- All subjects will be observed for 30 minutes after vaccination and any unsolicited systemic AEs occurring during that time will be recorded as immediate unsolicited systemic AEs in the electronic case report form (CRF) (see [Section 4.3.2.3.1](#)).
- The subject's parent / guardian will record information in a diary card about solicited reactions from D0 to D07 after vaccination and unsolicited AEs from D0 to Visit 2. SAEs will be reported throughout the duration of the trial.
- The subject's parent / guardian will record information only about possible SAEs and MAAEs in a memory aid (MA) from Visit 2 until the 6-month (+14 days) telephone call.
- In addition, the subject's parent / guardian will be asked to notify the site immediately about potential SAEs at any time during the trial.
- Staff will contact the subject's parent / guardian by telephone on D08 (+2 days) to identify the occurrence of any SAE not yet reported and to remind them to complete the diary card up to Visit 2 and to bring it back at Visit 2.
- The completed diary card will be reviewed with the subject's parent / guardian at Visit 2.

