**This call is made 8 to 10 days after the vaccination at Visit 1. If D08 (+2 days) falls on a weekend or holiday, the telephone call may be made on the following business day. During this telephone call, the staff will find out whether the subject experienced any SAE not yet reported, and will remind the subject's parent/guardian to continue using the diary card up to Visit 2, to bring the diary card to the study center at Visit 2, and confirm the date and time of Visit 2.

††Staff will contact the subject's parent/guardian by telephone at 6 months (180 days +14 days) after vaccination at Visit 1 to identify the occurrence of any MAAEs as well as SAEs not yet reported.

‡‡MAAEs that occur between Visit 1 and Visit 2 will be recorded as unsolicited AEs.

§§

***The MA is used for the recording of SAEs and MAAEs. The site staff will make a telephone call to the parent/guardian to obtain the information 180 days (+14 days) after the vaccination at Visit 1. Since the timeframe between Visit 1 and Visit 2 (inclusive) will be captured in the diary card, the MA will be used to collect SAE and MAAE data from Visit 2 to TC2.

4 Endpoints and Assessment Methods

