4.3.2.2 Safety Endpoints

The observational endpoints for the evaluation of safety are:

- Occurrence, nature (Medical Dictionary for Regulatory Activities [MedDRA] preferred term), duration, intensity, and relationship to vaccination of any unsolicited systemic AEs reported in the 30 minutes after vaccination.
- Occurrence, time of onset, number of days of occurrence, intensity, action taken, and whether the reaction led to early termination from the study, of solicited (prelisted in the subject's diary card and electronic case report form [CRF]) injection site reactions occurring up to 7 days after vaccination.
- Occurrence, time of onset, number of days of occurrence, intensity, action taken, and whether the reaction led to early termination from the study, of solicited (prelisted in the subject's diary card and CRF) systemic reactions occurring up to 7 days after vaccination.
- Occurrence, nature (MedDRA preferred term), time of onset, duration, intensity, action taken, relationship to vaccination (for systemic AEs only), and whether the event led to early termination from the study, of unsolicited AEs up to Visit 2 after vaccination.
- Occurrence, nature (MedDRA preferred term), time of onset, duration, seriousness criteria, relationship to vaccination, outcome, and whether the SAE led to early termination from the study, of SAEs ██████████ throughout the trial.
- Occurrence, nature (MedDRA preferred term), time of onset, duration, seriousness, relationship to vaccination, and outcome for MAAEs from Visit 2 to the 6-month follow-up contact. MAAEs will be collected as unsolicited AEs up to Visit 2.

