4.3.2.3 Unsolicited Non-serious Adverse Events From Day 0 to Day 30 After Vaccination

In addition to recording solicited reactions, parents / guardians will be instructed to record any other medical events that may occur during the 30-day period after vaccination. Space will be provided in the diary card for this purpose.

For each unsolicited non-serious AE, the following information is to be recorded:

- Start and stop dates^a
- Intensity of the event:
 - For measurable unsolicited non-serious AEs that are part of the list of solicited reactions, the size of the AE as well as the temperature for fever will be collected and analyzed based on the corresponding scale used for solicited reactions (see [Table 4.1](#) and [Table 4.2](#))
 - Other unsolicited non-serious AEs will be classified according to the following intensity scale:
 - Grade 1: No interference with activity
 - Grade 2: Some interference with activity
 - Grade 3: Significant; prevents daily activity
- Action taken for each AE, if any (e.g., medication)

The action taken by the parent or guardian to treat any unsolicited AEs will be classified in the CRF using the following scale:

- 0: None
- 1: Medication (self-medication with an existing prescription or over-the-counter medication)
- 2: Health care provider contact (no new medication prescribed)

^a The stop date of all related AEs will be actively solicited. For other events, the investigator will provide the stop date when it becomes available. AEs for which no stop date was obtained during the course of the trial will be considered as ongoing at the end of the trial.

unsolicited AEs collected for this post-vaccination period. MAAEs that occur from Visit 2 (D30 [+14 days]) to D180 (+14 days) will be recorded as such in the memory aid. An MAAE that occurs within the study period but meets the definition of an SAE should be reported only on the SAE Reporting Form, but not on the MAAE page of the CRF. The Investigator will assess the causal relationship between the MAAE and the investigational or study product as either “Not related” or “Related”, as described in [Section 4.3.2.3.7](#).

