5.1.3.2.2 Safety

Safety results in [Section 4.3.2.2](#) will be described for subjects in all study groups. The main parameters for the safety endpoints will be described by 95% CIs (Clopper-Pearson method) (6). Analyses will contain at least the descriptions listed in [Table 5.2](#):

Table 5.2: Statistical analyses for safety observational objective

Safety Events	Time and Group	Description
Immediate unsolicited systemic AE	Within 30 minutes after injection for all subjects in Groups 1 and 2 at D0	Percentage of subjects that have the event, MedDRA terms, intensity, relationship to vaccine, study discontinuation
Solicited injection site reactions	Up to 7 days after D0 for all subjects in Groups 1 and 2	Percentage of subjects that have the event, onset, duration, intensity, action taken, study discontinuation, temperature collection routes
Solicited systemic reactions	Up to 7 days after D0 for all subjects in Groups 1 and 2	
Unsolicited AE	Up to 30 days after D0 for all subjects in Groups 1 and 2	Percentage of subjects that have the event, MedDRA terms, onset, duration, intensity, relationship, action taken, study discontinuation

^a rSBA vaccine seroresponse is defined as a post-vaccination titer $\geq 1:32$ for subjects with pre-vaccination rSBA titer $< 1:8$, or a post-vaccination titer ≥ 4 times the pre-vaccination titer for subjects with pre-vaccination rSBA titer $\geq 1:8$.

SAE [REDACTED]	Up to 6-month follow-up after D0 for all subjects in Groups 1 and 2	Percentage of subjects that have the event, MedDRA terms, onset, duration, relationship, seriousness criteria, outcome, study discontinuation
MAAE	Between Visit 1 and Visit 2 for all subjects in Groups 1 and 2 (as unsolicited AE) From Visit 2 to 6-month follow-up for all subjects in Groups 1 and 2	Percentage of subjects that have the event, MedDRA terms, onset, duration, intensity, relationship, action taken, study discontinuation

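### Unsolicited adverse events are an endpoint to Visit 2 (D30 to D44) but are tabulated only to D30, and the MAAE section borrows that cut-off without disapplying it

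*SAP*

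**What the plan says.** **Endpoint and collection.** SAP Section 4.3.2.2 defines the endpoint in terms "of unsolicited AEs up to Visit 2 after vaccination". Section 3.1 sets collection from Visit 1 to Visit 2, with Visit 2 at D30 plus up to 14 days. Section 3.2 has parents record in the diary card "unsolicited AEs from D0 to Visit 2", and Table 3.2 shows the same period. A footnote to that table says that "the timeframe between Visit 1 and Visit 2 (inclusive) will be captured in the diary card".

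**Analysis.** Section 4.4.1.2.4 analyses unsolicited non-serious events within 30 days, "which corresponds to AEs with a time of onset between 0 and 30 days after vaccination or missing". Later events "with a time of onset higher than defined above will not be included in analysis, but will be listed separately". The unsolicited AE row of Table 5.2 (Section 5.1.3.2.2) reads "Up to 30 days after D0 for all subjects in Groups 1 and 2".

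**A shorter recording period.** The section on unsolicited non-serious events from Day 0 to Day 30 (4.3.2.3.3 in the table of contents) asks parents to record "any other medical events that may occur during the 30-day period after vaccination".

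**MAAEs.** Before Visit 2, MAAEs are recorded only as unsolicited events. From Visit 2 to the 6-month call they go into the memory aid. Section 4.4.1.4 and Table 5.2 give two visit-based periods, Visit 1 to Visit 2 and Visit 2 to the 6-month follow-up. Section 4.4.1.4 then says that the calculation methods are those of Section 4.4.1.2, which contains the 30-day exclusion.

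**The concern.** An endpoint and the analysis that reports it should cover the same period. Here the endpoint is longer, and the derivation rule sends the difference to a listing. A listing gives no percentages or confidence intervals by group, which is the form that Table 5.2 plans for unsolicited events.

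The cross-reference in Section 4.4.1.4 raises a second problem. It cannot be applied as written without contradicting the MAAE periods in the same section and in Table 5.2. A programmer would have to decide alone which parts of Section 4.4.1.2 carry over.

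At stake is whether the safety description, which is a stated trial objective, covers the period that it claims to cover.

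**Working it through.** **1. Unsolicited events: day count.** The inputs are Visit 2 on day v, with v from 30 to 44 (Section 3.1, Table 3.2), and an analysis window of D0 to D30, which is 31 calendar days (Section 4.4.1.2.4). Collected days are v + 1. Days collected but not tabulated are (v + 1) − 31 = v − 30. The untabulated share is (v − 30)/(v + 1).

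| Visit 2 day | Collected days | Not tabulated | Share |
|---|---|---|---|
| D30 | 31 | 0 | 0/31 = 0% |
| D37 | 38 | 7 | 7/38 = 18.4% |
| D44 | 45 | 14 | 14/45 = 31.1% |

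For the 1,000 planned children (500 per group) the range is 0 to 1,000 × 14 = 14,000 child-days. If Visit 2 falls on D37 on average, which is an assumption (the middle of the window), it is 1,000 × 7 = 7,000. The SAP gives neither a distribution of Visit 2 dates nor an event rate, so these are amounts of calendar time and not counts of events. The SAP states no figure of its own to reproduce.

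**2. Which late events drop out.** Two rules for missing onset disagree, and events with missing onset stay in the tables.
- Section 4.4.1.2.4: onset is missing only if the start date or the vaccination date is missing or partial.
- Section 5.3.1.5: onset is missing if the start date or the stop date is missing or partial.

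Take an event that starts on D35 with no stop date. Under Section 4.4.1.2.4 its onset is known to be day 35, so it is only listed. Under Section 5.3.1.5 its onset counts as missing, so it is tabulated. The SAP therefore does not settle the exact set of excluded late events.

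**3. Diary period.** Sections 3.1 and 3.2 and the Table 3.2 footnote run the diary to Visit 2, while the section on unsolicited non-serious events describes 30 days. If parents stopped at D30, later events would depend on the question about other events that Section 4.3.2.3 has the investigator ask at Visit 2. The memory aid would not fill the gap, because it starts at Visit 2.

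**4. MAAEs: two readings of Section 4.4.1.4.**
- *The visit-based periods govern.* Every MAAE from D0 to Visit 2, and from Visit 2 to the 6-month contact, falls in one of the two summaries. The gap is 0 days.
- *The imported methods are read literally.* Known onset after D30 is excluded throughout. With the 6-month contact on D180 to D194, this removes 180 − 30 = 150 to 194 − 30 = 164 days per child, before and after Visit 2 alike. It leaves almost nothing of the second MAAE summary that Table 5.2 plans.

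The second reading cannot be intended, but no sentence in the SAP rules it out.

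**The case against.** The strongest reply is that the 30-day analysis is deliberate. The derivation rule, Table 5.2 and a section heading all agree on it. Every child seen within the visit window has complete D0 to D30 coverage, so a fixed window gives equal observation time, while a window to Visit 2 varies by child. On that view the fault is one endpoint sentence that is too wide. This stands as a reason to keep the 0-to-30-day table. It does not remove the mismatch, because Section 4.3.2.2 still defines a longer endpoint.

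A reader might infer that late safety events disappear. The SAP does not support that. The events are listed, events with missing onset stay in, and Section 4.4.1.3.2 analyses serious events over the whole study as well as within 30 days.

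A reader might also infer that MAAEs with onset from D31 to Visit 2 fall into neither MAAE summary while those after Visit 2 are safe. That requires carrying the exclusion over to one period and not the other, and nothing in the text does so. The specific visit-based periods most naturally override the general cross-reference. What remains is a missing sentence, not a demonstrated gap.

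Finally, 31% should not be read as a share of events lost. It is calendar time, and it applies only to a child whose Visit 2 is on D44.

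**Conclusion.** The SAP is wrong as written, but the consequence is minor. For unsolicited non-serious events, the endpoint and the analysis differ by 0 to 14 days per child, and events with known onset in that interval are listed but not tabulated. The recording period and the missing-onset rule are each stated in two incompatible ways. For MAAEs, the cross-reference contradicts the visit-based periods if taken literally. Under the natural reading there is no gap.

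The effect is limited because these endpoints are descriptive, both groups are treated alike and the primary objective is untouched. The range of 0 to 14 days assumes that Visit 2 takes place within its window. How many events are involved cannot be derived from the SAP.

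**What to change.** 1. In Section 4.4.1.4, state that the 30-day exclusion in Section 4.4.1.2.4 does not apply to MAAEs. Define their two periods as onset from D0 to the actual Visit 2 date, and after Visit 2 to the 6-month contact.
2. Reconcile Section 4.3.2.2 with Section 4.4.1.2.4, Table 5.2 and the 30-day recording text. Keep the 0-to-30-day table as the main, equal-window display. Add one summary through Visit 2, labelled as having observation time that differs between children. At minimum, reword the endpoint to match the 30-day analysis and say that collection runs longer. Even then the diary text needs reconciling, because MAAEs before Visit 2 come only from the unsolicited event records.
3. Align Section 5.3.1.5 with Section 4.4.1.2.4 on when onset counts as missing, since this decides which late events are tabulated.

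The cost is SAP wording and one extra table. No new data are needed, because collection to Visit 2 is already planned, and Table 5.2 is stated as a minimum, so an added summary fits. The drawback is that the added table has a window whose length varies by child, hence the label.

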4.4.1.2.5 Duration

Duration is derived from the start and stop dates of the unsolicited non-serious AE provided in the clinical database:

- stop date of unsolicited non-serious AE - start date of unsolicited non-serious AE + 1.

The duration should be considered as missing only if one or both of the start and stop dates of the unsolicited non-serious AE is missing or partially missing.

4.4.1.3 SAEs

4.4.1.3.1 Last Vaccination

Last vaccination before any SAE is the study vaccination at V01.

4.4.1.3.2 Time of Onset

Time of onset will be computed using the same methodology as for unsolicited non-serious AEs described in [Section 4.4.1.2.4](#).

SAEs will be analyzed throughout the study using the following periods:

- During the study (i.e., all SAEs occurred during the study)
- Within 30 days after vaccination

An SAE with missing time of onset will be considered to have occurred just after the vaccination indicated by the visit number, so will be included in these tables.

Note: SAEs that occurred before vaccination (negative time of onset) will not be included in analysis, but will be listed separately.

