4.4.1.4 Medically-Attended Adverse Events

MAAEs that occur from Visit 1 (D0) to Visit 2 (D30[+14days]) will be recorded as unsolicited AEs on the diary card as part of all unsolicited AEs collected. Unsolicited AEs that have action taken categories 2 (health care provider contact) or 3 (Health care contact + Medication) will be summarized and presented as MAAEs between D0 visit and D30 visit.

MAAEs that occur from Visit 2 (D30 [+14 days]) to D180 (+14 days) will be recorded as such in the memory aid. An MAAE that occurs within the study period but meets the definition of an SAE should be reported only on the SAE Reporting Form, but not on the MAAE page of the CRF. Calculation methods are the same as unsolicited non-serious AEs as described in [Section 4.4.1.2](#).

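### An SAE whose start date lacks only the day is counted within 30 days of vaccination, even when its recorded month lies wholly after D30

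*SAP*

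**What the plan says.** The rule is spread over several sections of the SAP.

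- **3.1 Trial Design:** SAE information "will be collected throughout the study period from D0 through D180 (+14 days) after vaccination".
- **4.4.1.3.1:** "Last vaccination before any SAE is the study vaccination at V01". There is one dose, so a visit number can point to no other vaccination.
- **4.4.1.3.2:** for SAEs, "Time of onset will be computed using the same methodology as for unsolicited non-serious AEs described in" 4.4.1.2.4. Two periods are tabulated: the whole study, and "Within 30 days after vaccination".
- **4.4.1.2.4:** "The time of onset should be considered as missing only if one or both of the dates are missing or partially missing". The dates meant are the event's start date and the vaccination date.
- **4.4.1.3.2 again:** "An SAE with missing time of onset will be considered to have occurred just after the vaccination indicated by the visit number". The consequence is given in the same sentence: the event enters the tables for both periods. The only SAEs removed on timing are those with a negative time of onset.
- **5.3.1.5:** partial start dates of unsolicited AEs are not imputed, and events with missing onset are analysed by the visit at which they were collected.

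No section uses the month or year when those are known.

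**The concern.** Assuming early onset is reasonable when collection stops near D30, as it does for unsolicited non-serious AEs on the diary card. SAEs are followed about six times as long. After Visit 2 they reach the site through a memory aid, one telephone call at six months and spontaneous notification by the parent (SAP 3.2). A parent may recall the month of an event without the day. Under 4.4.1.3.2 such an event is treated as immediate, although the recorded month may exclude the first 30 days. That goes beyond a cautious guess under uncertainty, because it overrides information in the database.

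The figure at stake is the 30-day SAE count in each group, which will be read side by side for the two vaccines.

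**Working it through.** **1. Tracing the rule.** The SAP gives no figure to reproduce, so the check starts from an illustrative case: vaccination on 15 January of a non-leap year, SAE start recorded as June of that year, day unknown.

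- Earliest possible onset, 1 June: 16 + 28 + 31 + 30 + 31 + 1 = 137, so D137.
- Latest possible onset, 30 June: 137 + 29 = 166, so D166.
- By 4.4.1.2.4 the start date is partial, so onset is missing.
- By 4.4.1.3.1 and 4.4.1.3.2 the event is taken as just after V01 and enters both SAE tables.

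The event is reported within 30 days although every possible date lies at least 107 days after D30 (137 − 30).

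**2. How often the month settles the question.** Assumptions, none of them from the SAP: vaccination dates spread evenly over one calendar year (365 dates), onset uniform over each day of follow-up, day missing, month and year known. For every pair of vaccination date and onset day, the first and last day of the onset month were compared with D30.

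| Follow-up | Month wholly after D30 | Ambiguous | Month ends by D30 |
|---|---|---|---|
| D0-D180 | 74.7% | 16.3% | 9.0% |
| D0-D194 | 76.6% | 15.1% | 8.3% |

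The present rule puts 100% in the 30-day table. Using the month would put there 16.3 + 9.0 = 25.3% (to D180) or 15.1 + 8.3 = 23.4% (to D194). The true shares under the same assumption are 31/181 = 17.1% and 31/195 = 15.9%. The refined rule would therefore still err towards early onset, but by far less.

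**3. Effect of one event.** With the planned 500 per group (3.1) and the Clopper-Pearson limits that the SAP uses for safety:

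| SAE subjects within 30 days | Rate | 95% CI |
|---|---|---|
| 0 | 0% | 0 to 0.74% |
| 1 | 0.2% | 0.01 to 1.11% |
| 2 | 0.4% | 0.05 to 1.44% |

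Each misplaced subject adds 1/500 = 0.2 percentage points to one group.

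**4. Section 5.3.1.5 beside 4.4.1.3.2.** An SAE first collected at the six-month call could, by 5.3.1.5, be kept with that contact. By 4.4.1.3.2 it goes to V01 and into the 30-day table. Section 5.3.1.5 attaches no time window to a visit, and 4.4.1.3.2 is the text specific to SAEs, so the former does not override the latter. The two need reconciling.

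**The case against.** The best defence is that this is an open, prespecified worst-case convention, in line with 5.3.1.2, where missing causality counts as related. For late events it can only add SAEs to the 30-day table, and it applies equally to both groups. Parents are asked to report possible SAEs at once (3.2) and data are reviewed before lock (5.6), so partial dates should be few. Listings will show them as missing (5.3.1).

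Most of this stands, and it limits the weight of the point. It does not justify setting aside a recorded month. An added event raises one group's count only, so what is cautious for a single group need not be cautious when two are compared.

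A reader might infer more than the SAP supports:

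- **That 83% of day-missing SAEs are shown to be misplaced.** 150/181 = 83% is the share of follow-up days after D30. The share that the month alone can settle is 75-77%.
- **That one such SAE would double the 30-day count.** This needs an SAE rate that the SAP does not give.
- **That MAAEs after Visit 2 suffer the same error.** Section 4.4.1.4 does say "Calculation methods are the same as unsolicited non-serious AEs as described in" 4.4.1.2, but Table 5.2 reports MAAEs by two collection periods. Carrying over the 30-day window would exclude nearly every MAAE after Visit 2 with a known onset, so the window cannot be meant.
- **That SAEs from before vaccination will often slip in.** A missing onset does escape the negative-onset exclusion. But SAEs are collected from D0 and pre-existing conditions are not reported as AEs (4.3.2.1), so the case is remote.
- **That a missing stop date alone moves a late SAE into the 30-day table.** Section 5.3.1.5 says that a missing stop date makes onset missing for unsolicited AEs. For SAEs, 4.4.1.3.2 points to 4.4.1.2.4, which needs only the start and vaccination dates. This is a wording mismatch to settle.

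**Conclusion.** The point holds and is minor. Applied as written, 4.4.1.3.2 reports a day-missing SAE as within 30 days even when its month excludes that window, and 5.3.1.5 gives a different allocation without a window. Under uniform onset and evenly spread vaccination dates, about three quarters of day-missing SAEs (75-77%) would be placed wrongly although the recorded month shows it, and 15-16% could not be settled either way. The proportion would be lower if SAEs cluster soon after vaccination, and higher if the day is forgotten mainly for late events.

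The number of affected SAEs is not given and is probably small. The consequence is confined to one descriptive table, at 0.2 percentage points per subject in a group of 500. The during-the-study SAE table does not change for late events, and no safety hypothesis is tested.

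**What to change.** In 4.4.1.3.2, replace the sentence on missing onset with a rule that uses the known month and year. For a partial start date, find the earliest and latest possible dates, then:

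- if any possible date falls in D0-D30, or the date is wholly missing, count the SAE in both periods, which keeps the present conservative handling for ambiguous dates;
- if the earliest possible date is after D30, count it during the study only;
- if the latest possible date is before vaccination, list it separately with the other pre-vaccination SAEs.

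In 5.3.1.5, refer to this rule for SAEs, and state that onset depends on the start date and vaccination date, as in 4.4.1.2.4.

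The cost is a few sentences in the SAP and a few lines of derivation code. No new data are needed.
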